## **4. Study Design**

To examine the effect of narrative and non-narrative PWLs on visual attention, reactance, risk perceptions, and behavioral intentions, we will employ an online randomized experiment through the Qualtrics survey platform, which can be configured to redirect participants to Sticky by Tobii, a webcam-based eye-tracking platform. We plan to recruit adult moderate and heavy alcohol users via Prolific, a research company that provides online study panels. Participants will first be invited to participate in an online screening survey. Eligible participants will be invited to participate in the main experiment. In the main experiment, participants will first answer questions concerning baseline alcohol consumption and other background information. Then they will engage with a webcam-based eye-tracking task through Sticky by Tobii. Participants will first read instructions and tips related to completing the eye-tracking task. They will complete a brief calibration procedure and be presented with either three narrative PWLs or three non-narrative PWLs. Sticky by Tobii will record participants' gaze, thereby measuring visual attention to each PWL. After viewing each PWL, participants will answer a few questions. After viewing all three PWLs, they will answer questions based on all images combined. Upon study completion, participants will be compensated. A follow-up survey will be sent to participants after two weeks, which includes questions about their drinking behaviors and risk perceptions.

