## **5. Analytical Plan**

We will analyze the data using the statistical software SPSS. First, we will use descriptive statistics to provide study sample characteristics. Then, we will conduct independent-samples *t*-tests and chi-square tests to check whether there are differences in background variables (i.e., demographic characteristics and baseline alcohol consumption) between conditions. If there are a significant association between the experimental condition and a specific background variable(s), we will control for this variable(s) in all analyses. To test the first hypothesis, we will conduct multilevel mixed-effects linear regressions to examine the effect of narrative (vs. non-narrative) PWLs time until noticed, time viewed, and number of visits, and reactance. We will also control for repeated measures because each participant will view three PWLs that vary in cancer type within their assigned

condition. We will check the assumptions of these analyses. To test the second hypothesis, we will conduct independent-samples t-tests to examine the effect of PWLs type (narrative vs. non-narrative) on risk perceptions and behavioral intentions when there are no differences in the distribution of background variables between conditions. If there are differences in the distribution, we will conduct a series of analyses of covariance (ANCOVA). Assumptions of these analyses will be checked.

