**The main experiment:** Eligible participants will be invited to participate in the main experiment through the Prolific site. Once they sign up for the main experiment, they will be redirected to the online experiment built in Qualtrics survey platform. Participants will be first asked to sign the consent form and provided details about the study purpose and procedure. They will be informed that they will need to turn on their cameras when completing the eye-tracking task. Although their faces and surroundings will be recorded during the remote eye-tracking task, the researchers will not have access to these recordings. Consented participants will first answer several questions designed to measure baseline tobacco and alcohol consumption, alcohol-related knowledge, and the device they are currently using to be directed to the corresponding mobile or desktop-based eye-tracking experiment. Next, participants will engage with a webcam-based eye-tracking task. They will first read instructions and tips related to completing the eye-tracking task. They will then go through a calibration procedure to ensure good tracking. Participants will then be randomly assigned to view an order-randomized stimulus set containing either three narrative PWLs or three non-narrative PWLs. Narrative PWLs will contain photos of cancer

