patients, and non-narrative PWLs will include images of diseased organs. All PWLs will include a simple, clear warning statement (e.g., “WARNING: Drinking alcohol can cause oral cancer.”) to describe the specific cancer risk associated with alcohol. Within each warning type, one will focus on oral cancer, one on esophageal cancer, and one on larynx cancer. All three cancers have higher relative risks for moderate and heavy drinkers compared to other types of cancer linked to alcohol. Participants will be instructed that the image will be displayed for 20 seconds and that they need to stay as still as possible while viewing. After viewing each PWL, they will proceed to answer questions designed to measure perceived attention, reactance, and narrative construction within the eye-tracking platform. After viewing all three PWLs, participants will answer additional questions about their and affective and cognitive responses toward the warnings, alcohol-related cancer risk perceptions and behavioral intentions, and policy support for the warnings. They will then answer a few questions designed to collect socio-demographic information at the end of the study. Upon completion of the study, participants will be debriefed. They will be reminded that they will be invited to participate in a follow-up survey in two weeks. The entire duration of the main experiment is expected to be about 15 minutes, with 5 minutes spent on completing the eye-tracking portion and 10 minutes on answering questions via the Qualtrics survey platform.

**The follow-up survey:** Participants who completed the main experiment will be invited to participate in the follow-up survey after two weeks. The follow-up survey will include questions about their behaviors related to drinking and the labels in the past two weeks. Risk perceptions, intentions, and policy support measured in the main experiment will be measured again to assess the long-term effect of narrative (vs. non-narrative) PWLs. The entire duration of the follow-up survey is expected to be about 5 minutes.

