response to each PWL, affective and cognitive responses after viewing all PWLs, risk perceptions, intentions to reduce and stop drinking, and policy support. The primary outcomes include attention, reactance, risk perceptions, and intentions, as stated in the hypotheses. The secondary outcomes include avoidance, narrative construction, affective and cognitive responses (i.e., processing fluency, affect, cognitive elaboration, and retrospective reflection), attitudes toward alcohol, intentions to forgo alcohol, intentions to avoid the warnings, and policy support for the warnings. The secondary outcomes are measured to explore the underlying psychological mechanisms of narrative (vs. non-narrative) PWLs. See the attached questionnaire for the self-report questions. Here, we describe how attention will be measured with the eye-tracker. Specifically, attention to each PWL will be measured with three eye tracking statistics: time until noticed, time viewed, and number of visits. Three areas of interest (AOI) will be defined a priori for each PWL, including (1) warning image, (2) warning text, and (3) entire warning label. All AOIs are consistent in size and location on each stimulus. Time until noticed measures the time between stimulus onset and the arrival of the participant's gaze into a specific AOI, which often reflects an AOI's ability to grab visual attention relative to other elements of a stimulus. Time viewed measures the average amount of time spent on an AOI, and it signals attention and cognitive processing. Number of visits measures the total number of unique times the AOI was viewed, which is an indicator of interest. Finally, socio-demographics will include questions related to their age, biological sex, gender identity, ethnicity, race, education, household income, political ideology, medical statistics literacy, and cancer history.

**The follow-up survey:** The follow-up survey will include questions related to their behaviors in the past two weeks, including drinking behavior change due to the labels, information seeking behaviors, and social interactions. Risk perceptions, attitudes, intentions, and policy support assessed in the main experiment will be measured again in the follow-up survey.

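### The adjust-if-imbalanced rule can reach socio-demographic items asked after the labels; if the two label types shift such an item differently, adjusting for it can bias H1 and H2 in either direction

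*Combined protocol and SAP*

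**What the plan says.** Section 5 (Analytical Plan) checks for "differences in background variables (i.e., demographic characteristics and baseline alcohol consumption) between conditions", using t-tests and chi-square tests. For any variable significantly associated with condition, "we will control for this variable(s) in all analyses". For H2 this means that ANCOVA replaces the independent-samples t-test.

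Section 7 (Study Procedures, the main experiment) gives the order of events. Before the eye-tracking task, "Consented participants will first answer several questions designed to measure baseline tobacco and alcohol consumption, alcohol-related knowledge" and the device in use. Calibration, randomisation, the three labels and the outcome questions follow. Only then: "They will then answer a few questions designed to collect socio-demographic information at the end of the study".

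Section 7.1 (Data Collection/Instruments) lists the late block: "socio-demographics will include questions related to their age, biological sex, gender identity, ethnicity, race", then education and household income, and finally "political ideology, medical statistics literacy, and cancer history".

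No section limits the adjustment rule to variables measured before the labels.

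**The concern.** Covariate adjustment in a randomised comparison is safe when the covariate cannot have been affected by the assigned condition. Baseline alcohol consumption meets that requirement because it is asked before randomisation. Age, biological sex, race, ethnicity and education meet it in practice, although they are asked late. Political ideology, medical statistics literacy and self-reported cancer history are less secure, and gender identity possibly so. The first is an attitude, the second a literacy measure, and the third a self-report about the disease just shown. One arm has seen photographs of cancer patients and the other images of diseased organs.

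A significant difference between conditions in such an item could be chance imbalance or an effect of the labels. The rule treats both alike. Because it is triggered by significance, the more an item has been shifted, the more likely it is to be selected. The rule reaches every H1 and H2 analysis.

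**Working it through.** **Inputs from the protocol (section 6.2.1).** Enrolment of 800, alpha .05, 80% power, d = .20, independent t-test.

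**Assumptions.** Two-sided test and 1:1 allocation, so 400 per arm (neither is stated). The differential shift of the item between arms (δ, in SD) and its within-arm correlation with the outcome (ρ) are not in the documents, so a range is shown.

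**1. The plan's own figure.** n per arm = 2(1.96 + 0.842)²/0.20² = 392.4, so 393 per arm and 786 in total (788 with the t distribution). Power at 400 per arm is .807. The stated 800 is reproduced.

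**2. Chance that the rule selects one item.** The standard error of the arm difference is s = √(2/400) = .0707, and the critical difference is c = 1.96 × .0707 = .1386. P(select) = Φ((δ − c)/s) + Φ((−c − δ)/s).

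| Shift δ (SD) | P(select) |
|---|---|
| 0 | 5% |
| 0.05 | 11% |
| 0.10 | 29% |
| 0.15 | 56% |
| 0.20 | 81% |

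**3. Bias once the item is in the model.** The adjusted estimate is the outcome difference minus ρ times the item difference, so its expectation is .20 − ρδ. At ρ = .3 this is .20 − .03 = .17 for δ = 0.10, and .20 − .06 = .14 for δ = 0.20. Simulation (6,000 runs per scenario) gave .172 and .142.

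**4. Bias of the whole rule.** Step 3 conditions on selection. The planned procedure is a t-test or an ANCOVA according to the balance test, so the relevant average is over all trials:

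E(estimate) = .20 − ρ × E(item difference × selected).

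The last expectation equals .0535 at δ = 0.10 and .1808 at δ = 0.20. With ρ = .3:

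- δ = 0.10: .20 − .3 × .0535 = .184, a bias of .016, or 8% of d = .20.
- δ = 0.20: .20 − .3 × .1808 = .146, a bias of .054, or 27%.

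Two separate simulations gave .183 and .184 for the first, and .145 and .147 for the second. Multiplying P(select) by the bias in step 3 (.29 × .03 = .009 at δ = 0.10) understates this. Trials in which the item is not selected are those where its observed difference happened to be small, and their unadjusted estimates are pulled the same way.

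**5. Sensitivity over the whole rule (true d = .20).** Mean estimates follow from step 4; power comes from the 6,000-run simulation.

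| δ | ρ | Mean estimate | Power under the rule |
|---|---|---|---|
| 0 | .1 to .5 | .200 | .81 to .82 |
| +0.10 | .1 | .195 | .78 |
| +0.10 | .3 | .184 | .75 |
| +0.10 | .5 | .173 | .73 |
| +0.20 | .1 | .182 | .72 |
| +0.20 | .3 | .146 | .58 |
| −0.10 | .3 | .216 | .87 |
| −0.20 | .3 | .254 | .96 |

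The direction depends on the signs of ρ and δ. The higher power in the last two rows comes from an inflated estimate and is no gain.

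**6. H1.** The calculation follows the t-test or ANCOVA path of H2. The same mechanism applies to the H1 mixed models, but its size there was not computed.

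**The case against.** The strongest reply is that bias needs a *differential* shift between arms, and the documents show none. Both arms see three cancer warnings on the same three cancers and answer the same policy-support questions. Those shared exposures do not by themselves create a difference between arms. What would have to move the item is the contrast between patient and organ images. This stands: without a differential shift the bias is zero.

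The assumed shifts are also generous. The upper one, 0.20 SD, equals the effect for which the trial is sized on risk perceptions and intentions, the very outcomes the labels are meant to change. This stands too. At a 0.05 SD shift and a correlation of .3, the whole-rule mean is .195, a bias of about 3%.

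Section 5 speaks of demographic characteristics and does not say whether ideology, literacy and cancer history count. That is fair, but section 7.1 classes them as socio-demographics, so a reader applying the rule could include them. The ambiguity is itself a reason to name the covariates.

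It may also be said that section 4 (Study Design) has this asked early: "participants will first answer questions concerning baseline alcohol consumption and other background information". This does not rescue the plan. Section 7.1 describes the other pre-test background items as alcohol-related, and section 7 puts the socio-demographics at the end.

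A reader might infer two stronger claims. One is that the labels have already moved a background item; nothing in the documents supports that. The other is that the rule removes part of the effect; step 5 shows that it can equally inflate it.

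**Conclusion.** The point holds in conditional form. The stated rule can condition on a variable measured after exposure, and nothing in the plan prevents it. The exposed items are at most political ideology, medical statistics literacy, self-reported cancer history and possibly gender identity. The rest of the background set is asked before the labels or is effectively fixed, and age is also asked in the screener.

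At an assumed correlation of .3, the whole-rule bias is about 8% of d = .20 for a 0.10 SD differential shift and about 27% for 0.20 SD, in either direction. It is zero without a shift. The larger figures of 15% (.03/.20) and 30% (.06/.20) apply only to trials in which the item has entered the model, and should not be read as the bias of the planned procedure. Shift, correlation and 1:1 allocation are assumptions. No stated sample size changes. This is a cheap improvement.

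**What to change.** Add a statement to section 5 that covariate adjustment uses only:

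- variables measured before the labels (screener and pre-test items such as baseline alcohol consumption); and
- characteristics that exposure cannot change (age, biological sex, race, ethnicity, education).

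State also that political ideology, medical statistics literacy, cancer history and any other changeable item asked after the labels are used for description only. Assign gender identity and household income to one list or the other by name, so that no choice remains once the data are seen.

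Do not move questions to the pre-test now. Section 6.2.1 reports 404 participants already through the main experiment, about half of the 800 planned. A move would mix measurement before and after exposure, and would change what later participants answer before seeing the labels.

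The cost is a short addition to the text and slightly less covariate information. With only unaffected variables eligible, the simulated mean estimate stays at .200 and power at about .81 to .82.

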## 7.1. Data Collection/Instruments

The screening survey questionnaire, the main experiment questionnaire, the follow-up survey questionnaire, and the experimental stimuli (i.e., narrative and non-narrative PWLs) are included in the submission. Below, we briefly describe each questionnaire.

**The screening survey:** The screening survey will include five questions related to their age, average weekly alcohol consumption, and technical support to complete eye tracking tasks.

**The main experiment:** *Pre-test measures* will assess baseline tobacco and alcohol consumption and other alcohol-related background information. Baseline tobacco and alcohol consumption are included because the combination of tobacco and alcohol significantly increase the risk for developing cancers in mouth, esophagus, and larynx, the three cancer types shown in the experimental stimuli. Other *alcohol-related background information* will be included because they may influence how participants respond to the experimental stimuli. *Post-test measures* will assess visual attention measured via the eye-tracker and a self-report question, avoidance, narrative construction, and reactance in

response to each PWL, affective and cognitive responses after viewing all PWLs, risk perceptions, intentions to reduce and stop drinking, and policy support. The primary outcomes include attention, reactance, risk perceptions, and intentions, as stated in the hypotheses. The secondary outcomes include avoidance, narrative construction, affective and cognitive responses (i.e., processing fluency, affect, cognitive elaboration, and retrospective reflection), attitudes toward alcohol, intentions to forgo alcohol, intentions to avoid the warnings, and policy support for the warnings. The secondary outcomes are measured to explore the underlying psychological mechanisms of narrative (vs. non-narrative) PWLs. See the attached questionnaire for the self-report questions. Here, we describe how attention will be measured with the eye-tracker. Specifically, attention to each PWL will be measured with three eye tracking statistics: time until noticed, time viewed, and number of visits. Three areas of interest (AOI) will be defined a priori for each PWL, including (1) warning image, (2) warning text, and (3) entire warning label. All AOIs are consistent in size and location on each stimulus. Time until noticed measures the time between stimulus onset and the arrival of the participant's gaze into a specific AOI, which often reflects an AOI's ability to grab visual attention relative to other elements of a stimulus. Time viewed measures the average amount of time spent on an AOI, and it signals attention and cognitive processing. Number of visits measures the total number of unique times the AOI was viewed, which is an indicator of interest. Finally, socio-demographics will include questions related to their age, biological sex, gender identity, ethnicity, race, education, household income, political ideology, medical statistics literacy, and cancer history.

**The follow-up survey:** The follow-up survey will include questions related to their behaviors in the past two weeks, including drinking behavior change due to the labels, information seeking behaviors, and social interactions. Risk perceptions, attitudes, intentions, and policy support assessed in the main experiment will be measured again in the follow-up survey.

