#### 6.2.1. Sample Size

No previously published work has examined the effect of narrative (vs. non-narrative) PWLs on visual attention and reactance. In our preliminary work, we conducted an online experiment testing the effect of PWLs type among adult moderate and heavy drinkers. We found that participants who saw non-narrative PWLs reported significantly higher reactance to the warnings than those who saw narrative PWLs ( $r = .19$ ).

Therefore, in the proposed project, we will use the effect size of  $r = .19$  to estimate the sample size. With the alpha level set at .05, we will need 213 participants to achieve a statistical power of .80. The final sample size needs to account for possible failure to (1) complete the eye-tracking task and (2) generate usable eye-tracking data for those who complete the task. Based on a recent remote eye-tracking study (Chen-Sankey et al., 2023) and information provided by the Sticky by Tobii team, we plan to screen 1,200 participants (41% rate of completion) and enroll 500 participants (43% rate of usable data).

Because risk perceptions and behavior intentions are also our primary outcomes, we conducted an additional power analysis to calculate the sample size for these two

outcomes. Based on previous research (e.g., Oschatz & Marker, 2020), narratives had a small effect on persuasion. With the alpha level set at .05, we would need at least 800 participants to detect an effect of  $d = .20$  with 80% power in an independent t-test.

Given that the sample size to detect a significant effect on risk perceptions and behavior intentions ( $N=800$ ) is larger than that on reactance ( $N=500$ ), we decided to enroll 800 participants in our main experiment. Accordingly, we would need to screen 1,951 participants (41% rate of completion).

Running the study resulted in 1,045 eligible participants from 1,922 screened participants. Of the 1,045 eligible participants, only 404 participants so far completed the main experiment successfully. Increasing the screener eligibility to 3,000 is expected to increase the successful completion of the main study to the projected 800.

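### H1 rests on four to ten primary tests with no error control, lead gaze measure or success rule; H2 also lacks a success rule, and its power depends on which one is chosen

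*Combined protocol and SAP*

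**What the plan says.** Section 7.1 makes four constructs primary: "The primary outcomes include attention, reactance, risk perceptions, and intentions, as stated in the hypotheses". It then splits attention: "attention to each PWL will be measured with three eye tracking statistics: time until noticed, time viewed, and number of visits". It adds: "Three areas of interest (AOI) will be defined a priori for each PWL". The three areas are the image, the text and the whole label.

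Section 5 plans mixed-effects regressions for the three gaze measures and for reactance, and does not mention AOIs. For the other hypothesis it says: "To test the second hypothesis, we will conduct independent-samples t-tests to examine the effect of PWLs type", with risk perceptions and behavioral intentions as outcomes. ANCOVA replaces the t-test if background variables differ between conditions. Section 5 does not say whether intention to reduce and intention to stop are tested separately.

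Section 3.3 states both hypotheses directionally and joins their components with *and*. An alpha level appears only in Section 6.2.1: "With the alpha level set at .05, we will need 213 participants to achieve a statistical power of .80" (reactance, r = .19), and "With the alpha level set at .05, we would need at least 800 participants to detect an effect of" d = .20 with 80% power. The second calculation is introduced with: "Because risk perceptions and behavior intentions are also our primary outcomes".

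The text supplied contains no multiplicity adjustment, testing order, lead outcome or rule for when H1 or H2 counts as supported. Text between Section 10 and Section 11.2 was removed from the copy reviewed, so this absence is asserted for the rest only.

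**The concern.** Each hypothesis covers several outcomes, and the plan leaves open which results decide it. The choice is widest for H1: any of three gaze measures, on any of three AOIs, could be put forward as the attention finding, with reactance alongside. If one favourable result can be reported as support, the .05 used to size the study is not the error rate of the conclusion about H1 or H2. If instead every component must be significant, the error rate is safe, but the 80% power quoted for H2 is not the power of the H2 conclusion. The sponsor needs to settle this before outcomes are analysed; Section 6.2.1 already reports 404 completed participants.

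**Working it through.** **Step 1: alpha and sidedness.** Section 5 gives neither, so both are inferred from Section 6.2.1.
- r = .19: d = 2r/√(1−r²) = .38/.982 = 0.387. N = 4(1.960+0.842)²/0.387² ≈ 210; noncentral t gives 212 and Fisher z gives 215. The plan says 213. One-sided formulas give 166-170.
- d = .20: N = 4(1.960+0.842)²/.20² ≈ 786; noncentral t gives 788. The plan says at least 800, where power is 80.7%. One-sided gives 620.

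Only two-sided .05 reproduces the plan's figures.

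**Step 2: number of tests.** H1 has four outcomes in Section 5 (three gaze measures and reactance). With every AOI tested it has 3 × 3 + 1 = 10. H2 has two constructs, or three tests if the two intentions are separate. The self-report attention item in Section 7.1 could add one to H1, and the two-week repeats could add to H2.

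**Step 3: chance of at least one false rejection.** Every outcome is coded so that positive favours narrative labels, and no effect exists.
- Independent tests, hypothesised direction: 1 − .975^k. Either direction: 1 − .95^k.
- Common correlation ρ, hypothesised direction: 1 − ∫φ(u)[Φ((1.96 − √ρ·u)/√(1−ρ))]^k du. For either direction, subtract the matching lower-tail term inside the bracket.

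| Tests | Hypothesised direction, ρ = 0 / .7 / .9 | Either direction, ρ = 0 / .7 / .9 |
|---|---|---|
| H1, 4 | 9.6% / 6.5% / 4.7% | 18.5% / 13.0% / 9.4% |
| H1, 10 | 22.4% / 10.7% / 6.4% | 40.1% / 21.3% / 12.8% |
| H2, 2 | 4.9% / 4.2% / 3.5% | 9.8% / 8.3% / 7.0% |
| H2, 3 | 7.3% / 5.5% / 4.2% | 14.3% / 10.9% / 8.4% |

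A single test gives 2.5% in the hypothesised direction and 5% in either. As a check, simulating ten H1 tests with higher correlation between AOIs of the same measure, and low correlation with reactance, gave 12-18% in the hypothesised direction. That lies inside the ten-test range for ρ of 0 to .7.

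**Step 4: cost of controlling H1.** With two confirmatory tests the strictest Hochberg or Holm step is .025 (critical value 2.24). The plan sizes H1 on r = .19, so d = 0.387.
- Gaze: 43% usable data in Section 6.2.1, and .43 × 800 = 344 records. Noncentrality 0.387 × √(344/4) = 3.59, so power ≈ Φ(3.59 − 2.24) = 91%.
- Reactance at 800: 0.387 × √200 = 5.47, so power ≈ Φ(5.47 − 2.24), over 99%.

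**Step 5: H2 power under each rule.** N = 800, d = .20, noncentrality .20 × √200 = 2.83, correlation .3 to .7 where simulated.
- Each outcome at .05, unadjusted: 81%.
- All three significant: about 58-67%.
- Hochberg across three, per outcome: about 76% if all three effects exist, about 70% if two, 67% if one. Holm gives 74-75% if all three exist.
- Flat .05/3: Φ(2.83 − 2.39) ≈ 67%; about 1,048 participants would be needed for 80%.

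**The case against.** The strongest reply is that Section 3.3 joins the parts of each hypothesis with *and*. Read literally, every part must be significant, and the chance of false support is then at most 2.5% in the hypothesised direction, with no inflation. Alternatively, each outcome is its own claim and .05 is the right rate for each. Both readings are fair, but the plan states neither. The literal reading also moves the problem to power, since all three H2 outcomes would then reach significance together only 58-67% of the time.

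A reader might infer that about 13 primary tests are planned, and that claiming support carries a false-positive chance of 21-40% for H1 and 11-14% for H2. The documents do not support that. Those figures count rejections in either direction, whereas both hypotheses are directional and a result favouring non-narrative labels would contradict them. They also test every AOI, although Section 5 never mentions AOIs, and they assume a one-result rule that the plan does not contain. Correlations above .7 are plausible because the whole-label area contains the other two, and they lower the rates.

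On cost, it can be objected that testing reactance at .025 with 213 participants gives power of only about Φ(0.387 × √(213/4) − 2.24) = 72%. Section 6.2.1, however, moves the enrolment target to 800, although Section 11.2 still carries 500 and 213. For H2 the cost objection stands: any adjustment takes per-outcome power below the 80% for which 800 was chosen.

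**Conclusion.** The gap is real. H1 has at least four primary tests, and ten if every AOI is tested. No error control, lead gaze measure or success rule appears in the text supplied. If any one significant result in the hypothesised direction counts as support, the false-support chance for H1 is about 7-10% with four tests or 11-22% with ten, against 2.5% for one test. For H2 it is about 4-5% with two tests or 5.5-7% with three, a much smaller excess.

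These figures assume the one-result rule, two-sided .05 (inferred from the sample-size section) and correlation between 0 and .7. None of these is stated in the analysis plan. The power figures assume that 800 participants are reached and, for gaze, that the reactance effect of r = .19 carries over, as the plan's own sizing does.

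Controlling H1 is a cheap improvement. For H2 the firm requirement is to state a rule with power that matches it; whether to adjust is a judgement for the sponsor.

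**What to change.** **H1, in Section 5, before outcomes are analysed.** Name one gaze measure on one AOI as confirmatory (for example, time viewed on the entire label). Apply Hochberg or Holm across that measure and reactance at two-sided .05. Report the other gaze tests, including the remaining AOIs, as supportive. State the alpha level and sidedness, say what counts as support for H1, and say whether the self-report attention item is confirmatory. The cost is wording, plus a small loss of power at the .025 step, which still leaves about 91% for gaze and over 99% for reactance.

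**H2, in Sections 5 and 6.2.1.** State whether the two intentions are separate tests, which time point is primary, and whether support needs all outcomes or any one. Restate power at N = 800 to match:
- All three required: about 58-67%.
- Hochberg across three: about 76%, 70% or 67% per outcome, according to whether three, two or one of the effects exist.
- No adjustment: keep 81% per outcome, report each H2 outcome as a separate claim at .05, and make no overall claim from a single result.

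None of these needs extra participants unless the sponsor wants to adjust H2 and keep 80% power; at .05/3 that would take about 1,048.
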